7.4 Progression Free Survival

The PFS is defined as time from the first day of treatment to the first documented disease progression per RECIST 1.1 or death, whichever occurs first. Subjects who have not progressed at the time of analysis will be censored at the latest date of assessment from their last evaluable disease assessment. The censoring guidance and the date of PD/death or censoring are given in the

Table 4. PFS will be summarized using Kaplan-Meier method if data warrants. Individual PFS will be listed for the All Treated population.

Table 4. Summary of Censoring Guidelines for PFS based on RECIST1.1

Situation	Date of PD/Death or Censoring	PFS Outcome
Documented PD or death	Date of the PD or death, whichever comes first	Event (unless the censoring rule specified below)
Death or PD immediately after ≥ 2 consecutive missed or non-evaluable disease assessments ¹ as per the protocol specified assessment schedule	Date of last evaluable disease assessment prior to missed or non-evaluable assessments, or the first dose of investigational product, whichever occurred last	Censored
No PD or death at time of analysis or lost to follow-up	Date of last evaluable disease assessment	Censored
No baseline disease assessment OR no post-baseline disease assessment AND no death prior to second scheduled post-baseline disease assessment	Date of first dose	Censored

¹ Two or more consecutive disease assessments is defined as $\geq 16+1$ weeks for the first 6 months or $\geq 24+1$ weeks for 6-24 months (two disease assessments as per protocol plus a one week visit window) after the last evaluable post-baseline disease assessment. If a subject has two or more consecutive missed or non-evaluable assessments followed by an assessment showing no radiologic disease progression, then the assumption will be that the subject did not progress during the missed or non-evaluable assessments.

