- 1) **At screening:** The following testing should be performed a) ABO and D group (ABO/Rh) type and antibody screen and antibody identification if required; b) DAT; c) Phenotype/genotype for, at a minimum, the minor antigens Rh C/c E/e, K, Jk, Fy and MNsS.
- 2) **C1/D2:** only need to perform blood phenotyping (ABO/Rh) and DAT.

- i. **Antiviral Testing:** Please see exclusion criterion 19 in Section 4.2. These tests will be performed at local laboratories according to the laboratory's normal procedures.
- j. **Tumor Assessment:** Tumor assessments are required for all subjects within 28 days prior to the first dose of SL-172154. The same method of assessment and the same technique should be used to characterize each identified and reported lesion at baseline, on treatment and during follow-up. Baseline and on-treatment tumor assessments by RECIST v1.1 should include CT with contrast of chest, abdomen, and pelvis and clinical examination (if applicable) of all known sites of disease at each time point. Bone scan, positron emission tomography (PET)/CT, and/or MRI should be performed if clinically indicated. Tumor lesions will only be considered measurable by clinical examination when they are superficial, and dimensions are accurately assessed using calipers or rulers. For skin lesions assessed by clinical examination, documentation by color photography including a ruler to estimate the size of the lesion, is required at all time points. Please refer to Section 8 for requirements regarding disease assessment. Tumor assessments must be performed at screening and at the following intervals until disease progression: approximately every 6 weeks through week 54 (e.g., C3D1, C5D1, C7D1), every 12 weeks up to year 2 (prior to cycles 23, 27, 31, and 35), and then every 24 weeks (prior to cycles 43, cycle 51, etc.) up to conclusion of the study. Confirmatory scans should be performed at least 4 weeks (>28 days) after initial documentation of an objective response and preferably at the next scheduled tumor assessment visit that is about 6 weeks later. Subjects who discontinue study treatment for reasons other than disease progression (e.g., AE) will be monitored for response until start of another anti-cancer therapy, disease progression, withdrawal of consent, death, or end of the study, whichever occurs first.

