7. EFFICACY ANALYSES

The efficacy endpoints include objective response, TTR, DOR, PFS, and change from baseline lesion diameter for injected lesion and non-injected lesions. All efficacy endpoints are based on the investigator disease assessment per RECIST 1.1. The efficacy analyses will be based on the All Treated population and Response Evaluable population. Unless specified otherwise, all efficacy data summaries will be presented by dose levels/cohorts, cancer type and all subjects in the analysis population.

Disease assessment will be performed at baseline (screening visit) and at the following intervals until disease progression: every 6 weeks until week 54, every 12 weeks up to year 2, and every 24 weeks until study conclusion. Confirmatory scans should be performed at least 4 weeks (>28 days) after initial documentation of an objective response and preferably at the next scheduled disease assessment that is 6 weeks later. If subjects discontinue study treatment prior to progressive disease, they should continue to be followed with radiologic disease assessments until disease progression, start of a new anti-cancer therapy, withdrawal of consent or death, whichever is earlier.

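### The 17- and 25-week limits in SAP Table 4 footnote 1 do not match this trial's scan schedule, so some progressions and deaths that row 2 censors would count as PFS events

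*SAP*

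**What the plan says.** Table 4 in SAP 7.4 censors PFS when progression or death comes immediately after at least two consecutive missed or non-evaluable assessments, counted "as per the protocol specified assessment schedule". The censoring date is the last evaluable assessment before the gap "or the first dose of investigational product, whichever occurred last".

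Footnote 1 gives the working definition: "Two or more consecutive disease assessments is defined as $\geq 16+1$ weeks for the first 6 months or" at least 24+1 "weeks for 6-24 months (two disease assessments as per protocol plus a one week visit window) after the last evaluable post-baseline disease assessment".

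The scan schedule is stated in SAP 7 as "every 6 weeks until week 54, every 12 weeks up to year 2, and every 24 weeks until study conclusion". Protocol 6.1 (SOA footnote j) agrees and ties the later scans to cycles: "every 12 weeks up to year 2 (prior to cycles 23, 27, 31, and 35". SOA footnote b gives assessments more than 3 weeks apart a window of plus or minus 1 week.

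On use of the endpoint, SAP 7.4 says "PFS will be summarized using Kaplan-Meier method if data warrants". Section 12 plans one PFS output, Listing 16.2.6.6.

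**The concern.** The footnote describes its limits as two protocol assessments plus one week. Sixteen weeks is two assessments only if scans are 8-weekly, and neither document has an 8-weekly schedule. Twenty-four weeks is two assessments only where scans are 12-weekly. That starts after week 54, whereas the footnote applies it from month 6.

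A limit that is too long lets a subject pass through two or three missed scans and still be scored as an event on the late date. Row 2 would censor that subject at the last evaluable scan. The subject then stays at risk through a period without evaluable scans, and the event is dated at its end.

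The footnote also does not say whether its 6-month cut refers to the last scan or to the event, so two programmers could derive different PFS statuses from the same data.

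**Working it through.** **Inputs.** C3D1 is week 6, and day 1 of cycle n falls at week 3(n − 1). Cycles 23, 27, 31 and 35 are therefore weeks 66, 78, 90 and 102. Scheduled scans are at weeks 6, 12, …, 54, 66, 78, 90 and 102. Each has a window of ±1 week. Month 6 is 365.25/2/7 = 26.1 weeks.

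**The plan's figures.** The stated formula is 2 × interval + 1 week.
- 17 weeks needs an interval of (17 − 1)/2 = 8 weeks, which is not in the documents. The 6-weekly schedule gives 2 × 6 + 1 = 13.
- 25 weeks = 2 × 12 + 1, correct only where scans are 12-weekly.

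**The formula on this schedule.** For a last evaluable scan at week L, the limit is (second following scan + 1) − L.

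| Last evaluable scan | Next two scans | Formula gives | Footnote, bands by last scan |
|---|---|---|---|
| Weeks 6–24 | L+6, L+12 | 13 | 17 |
| Weeks 30–42 | L+6, L+12 | 13 | 25 |
| Week 48 | 54, 66 | 66 + 1 − 48 = 19 | 25 |
| Week 54 | 66, 78 | 78 + 1 − 54 = 25 | 25 |
| Weeks 66, 78 | L+12, L+24 | 25 | 25 |

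**Deaths.** The difference between the last two columns is the period in which a death follows two missed scans but counts as an event: 13 to <17 weeks after last scans at weeks 6–24, 13 to <25 weeks for weeks 30–42, and 19 to <25 weeks for week 48. There is none for last scans at weeks 54–78.

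**Progression at a scheduled scan, bands by last scan.** Comparing the footnote with row 2 for every pattern to week 102 gives four nominal conflicts:
- 30→48 and 36→54: two missed, gap 18 < 25.
- 30→54: three missed, gap 24 < 25.
- 42→66: two missed, gap 24 < 25.

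Move the last scan and the progression scan by −1, 0 or +1 week each (9 combinations):
- Gap 18 becomes 16–20, always below 25. The patterns 30→48 and 36→54 conflict in 9 of 9.
- Gap 24 becomes 22–26. The patterns 30→54 and 42→66 conflict in 6 of 9 (gaps 22–24) and are correctly censored in 3 of 9 (gaps 25–26).
- For last scans at weeks 6–24 with two missed, gap 18 is at least 17 and is correctly censored, except at gap 16 (1 of 9).

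**Bands by event date.** The nominal conflicts rise from 4 to 11: 6→30, 12→30, 12→36, 18→36, 18→42, 24→42, 24→48, 30→48, 30→54, 36→54 and 42→66. Each has a gap of 18 or 24 weeks, below 25.

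**The other direction.** With a last scan at week 66, only week 78 missed, and progression at week 91, the gap is 25 and the footnote censors after a single missed scan. For last scans at weeks 54, 66 or 78 with one missed scan, this happens in 3 of 9 window combinations.

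**The case against.** The strongest reply concerns consequence. PFS is exploratory, Kaplan-Meier is conditional, and no PFS table or figure is planned. Enrollment stopped early in a study planned for about 18 subjects. The individual response listings let a reader check any subject's status. The nominal conflicts need a last evaluable scan at weeks 30–42, then two or three missed scans, then progression. The protocol's background cites median PFS of 2–3 months for older second-line options in HNSCC and 4.1 months for cetuximab in CSCC. Those populations are not identical, but such patterns should be rare. All of this stands and bounds the importance of the point.

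Two technical replies also have force. With bands read by last scan, scheduled-scan progression in the first 6 months is almost unaffected. And the week 66→91 case is a weakness of any fixed limit, because 25 weeks is what the formula gives there.

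The enumeration stops at week 102. Cycles 43 and 51 put scans at weeks 126 and 150. With bands by last scan, 90→126 (gap 36) and 102→150 (gap 48) would be censored after one missed scan. That adds conflicts, though few if any subjects would be followed so long.

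It could be argued that the footnote simply defines row 2. That fails, because both row 2 and the footnote appeal to the protocol schedule, and the numbers contradict it.

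**Conclusion.** The point holds. On the documented schedule the 17-week limit follows from no interval in use, and the 25-week limit is correct only for last scans at weeks 54–78. With bands read by last scan and scans to week 102, four nominal progression patterns are scored against row 2, two of them throughout the visit windows. Deaths are mis-scored over gaps 4 to 12 weeks wide for last scans up to week 48. Read by event date, the nominal progression conflicts number 11.

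The practical effect is small, and the number of affected subjects cannot be computed from the documents. The study ends about 1 year after the last subject's C1D1, so the examples at weeks 66–91 can arise only in earlier-enrolled subjects. The footnote should still be corrected, because individual PFS will be listed for all treated subjects.

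A separate minor matter carries no weight here. For last doses at C2D1 or later, SAP 6.7 adds 14 days for discontinued subjects and 21 for those on treatment, with dosing every 21 days. No reason is given for 14, but the documents do not show that it is an error. For the same last dose, with no death and data cutoff at least 20 days later, the two formulas differ by 21 − 14 = 7 days.

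**What to change.** Replace the week limits in footnote 1 with a direct count, for example:

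> PD or death is censored if two or more consecutive protocol-scheduled assessments (6-weekly to week 54, 12-weekly to year 2, then 24-weekly; each with its ±1-week window) were missed or non-evaluable between the last evaluable assessment (scheduled or unscheduled) and the PD or death. An assessment counts as missed only when its window has closed. The censoring date is the later of the last evaluable assessment before the missed ones and the first dose.

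This removes the ambiguity about bands and keeps row 2's first-dose clause. A subject with only a baseline scan (up to 28 days before dosing), weeks 6 and 12 missed, and death at week 14 is censored at first dose. That agrees with row 4, which covers "no post-baseline disease assessment AND no death prior to second scheduled post-baseline disease assessment". The footnote's closing sentence, on a later scan without progression, can stay.

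Do not substitute a flat 13-week limit. With a last scan at week 12, only week 18 missed, and progression at week 25, the gap is 25 − 12 = 13, and one missed scan would be censored.

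In SAP 6.7, reconcile 14 and 21 days or state the reason for 14.

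The cost is SAP wording and one derivation that counts missed scheduled scans, plus one constant or sentence in 6.7. No new data are needed. Make the change before database freeze, or record it in the clinical study report as SAP section 1 provides.

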7.5 Change from Baseline for Injected and Non-injected Lesions

Change from baseline diameter for each individual injected and non-injected lesion will be provided in a data listing. The best percent change from baseline for each individual injected and non-injected lesion will be presented using a waterfall plot.

8. SAFETY ANALYSES

Unless specified otherwise, all safety data summaries will be presented by dose levels/cohorts and all subjects based on the All Treated population. Safety analyses will include Maximum Tolerated Dose (MTD) evaluation, AEs, laboratory test results (hematology, chemistry, coagulation), death, vital signs/pulse oximetry/weight, ECOG, cardiac evaluation (ECG), and blood phenotype (ABO/Rh) with direct antiglobulin test (DAT).

8.1 Maximum Tolerated Dose Evaluation

The Maximum Tolerated Dose (MTD) evaluation will be based on the DLT Evaluable Population. The number and percentage of subjects with DLT will be presented by dose level for dose escalation cohorts. The MTD level will be indicated in the summary.

The MTD will be estimated using isotonic regression (based on the DLTs observed in the DLT evaluable subjects). A MAD will be reported if the DLT rate never reaches $\geq 25\%$. Otherwise, an MTD will be reported. Isotonic regression is a way to estimate the MTD under the assumption that toxicity increases with dose. When using isotonic regression, the first step is to identify the doses where the dose-toxicity monotonicity assumption is violated. The DLT estimate is then adjusted for the violators such that the final estimate of the DLT rate increases with the dose. The target DLT rate is then used to select the MTD. For example, suppose that when the trial is completed, the observed DLT rates [<# subjects who experienced DLT]/[# evaluable subjects] at five dose levels are (0/3, 1/3, 0/3, 4/15, 2/4). In this example the observed DLT rate at Dose Level 2 (i.e., 1/3=33%) is higher than the observed DLT rate at Dose Level 3 (i.e., 0/3=0%). To adjust for this violation, the DLT estimates are replaced with their average, i.e., $(1/3+0/3)/2=1/6$, resulting in the isotonic regression DLT estimates (0/3, 1/6, 1/6, 4/15, 2/4) = (0%, 16.7%, 16.7%, 26.7%, 50%), which monotonically increases with the dose level. Based on this isotonic estimate, assuming that the trial goal is to find the dose with the DLT rate of 30%, Dose Level 4 will be selected as the MTD. If there are no violators of the dose-toxicity monotonicity assumption, isotonic regression directly uses the observed DLT rates as the final estimates for MTD selection. For subjects who undergo intra-subject dose escalation, only DLTs that occur during the DLT period on the subject's initial dose level the assignment will be used for MTD determination.

In the case of dose levels with estimated toxicity of equal distance (tied dose levels) from the target toxicity of 30%, the following approach will be used: among all tied dose levels the highest dose level with target toxicity $\leq 30\%$ will be selected, unless all tied dose levels have estimated toxicity $> 30\%$, in which case the lowest dose level will be selected.

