9.2.4 Safety Analyses

The safety evaluation will be based on the All Treated Population and the DLT evaluation will be based on the DLT evaluable population. DLTs will be summarized by dose level. Frequency tables will be used to describe safety and tolerability parameters AEs, irAEs, SAEs, fatal SAEs and AEs leading to discontinuation of SL-172154. Changes in toxicity grade for clinical chemistry and hematology will be summarized. Change from baseline QTcF will also be summarized. Graphs may also be presented where appropriate. AEs will be mapped to a Medical Dictionary for Regulatory Activities (MedDRA) preferred term and system organ classification. Laboratory abnormalities will be graded according to the NCI CTCTAE v5., if applicable. Concomitant medications will be coded using the World Health Organization Drug Dictionary.

MTD: The MTD will be estimated using isotonic regression (based on the DLTs observed in DLT evaluable subjects). Specifically, the MTD is the dose for which the isotonic estimate of the DLT rate is closest to the target DLT rate of 30%. If two or more doses tie for the smallest difference, perform the following rules:

- If the estimated DLT rate < 30% for all doses, then select the higher dose among the tied doses;
- If the estimated DLT rate for the tied doses are a combination of < 30% for and > 30%, then select the higher dose among the tied doses;
- If the estimated DLT rate > 30% for all dose, then select the lower dose among the tied doses.

A MAD will be reported if the observed DLT rate is <25% among all dose levels. Otherwise, an MTD will be reported.

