16. APPENDICES

16.1 mTPI-2 Dose Escalation Scenarios

See [Table 5](#) in Section [9.1](#) for dose escalation decision rules based on the total number of subjects evaluable for DLT and the number of DLTs observed.

For each dose level, subjects will be enrolled in cohorts of approximately 3 to evaluate DLT and make a dose escalation/stay/de-escalation decision based on decision rules in [Table 5](#) in Section [9.1](#) as the following steps:

- **Step 1:** The first cohort of at least 3 subjects will be enrolled and evaluated for DLT, and dose escalation/stay/de-escalation decision will be made among at least 3 DLT evaluable subjects. Assuming 3 subjects are DLT evaluable in cohort #1, the following decisions will be made based on the number of subjects with a DLT among the 3 DLT evaluable subjects:
 - If no subject with a DLT, dose escalate to the next higher dose level;
 - If 1/3 subject with a DLT, stay at the current dose level and move to step 2;
 - If 2/3 subjects with a DLT, dose de-escalate to next lower dose level;
 - If 3/3 subjects with a DLT, dose de-escalate to next lower dose level and the current dose level will never be used;
 - If the first 2 subjects experience a DLT before the third subject enrolls, then de-escalate to the next lower dose level and the current dose level will never be used.
- **Step 2:** As there is 1 subject with DLT among 3 DLT evaluable subjects in cohort #1, approximately 3 subjects will be enrolled and evaluated for DLT at the current dose in cohort #2. Assuming 3 DLT evaluable subjects in cohort #2, the following decisions will be made based on the number of subjects with DLT among the 6 DLT evaluable subjects from cohort #1 and cohort #2:
 - If 1/6 subjects with a DLT (no subject with a DLT in cohort #2), then dose escalate to the next higher dose level;
 - If 2/6 subjects with a DLT (1 subject with a DLT in cohort #2), stay at the current dose level and move to step 3;
 - If 3/6 subjects with a DLT (2 subjects with a DLT in cohort #2), dose de-escalate to next lower dose level;
 - If 4/6 subjects with a DLT (3 subjects with a DLT in cohort #2), dose de-escalate to next lower dose level and the current dose level will never be used.

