1. INTRODUCTION

This statistical analysis plan outlines the planned analyses for Protocol SL03-OHD-102: Phase 1 Dose Escalation Study of the Agonist Redirected Checkpoint, SL-172154 (SIRP α -Fc-CD40L), Administered Intratumorally in Subjects with Cutaneous Squamous Cell Carcinoma or Squamous Cell Carcinoma of the Head and Neck:

Protocol Version	Approval date
Version v0.0	28May2020
Version v1.0	10July 2020

The purpose of this analysis plan is to provide specific guidelines from which the analysis of this study will proceed. As of 24February2022, the study enrollment was prematurely discontinued. This SAP is updated to reflect the changes in the data analysis due to the premature discontinuation of the study.

All decisions regarding data analysis, as defined in this document, have been made prior to Database Freeze of the study data. Any deviations from these guidelines will be documented in the clinical study report.

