2. STUDY OBJECTIVES AND OUTCOME MEASURES

Objective	Outcome Measure
Primary Objectives	
To evaluate the safety and tolerability of ITI administration of SL-172154 and to identify the maximum tolerated dose (MTD) or maximum administered dose (MAD) of SL-172154	
Safety/tolerability outcomes include: incidence of all adverse events (AEs) and immune-related adverse events (irAE), serious adverse events (SAEs), fatal SAEs, dose limiting toxicity (DLT), AEs and irAEs leading to discontinuation, and changes in safety assessments (e.g., laboratory parameters, vital signs etc.) per National Cancer Institute Common Terminology Criteria for Adverse Events (NCI-CTCAE – version 5.0).
 
The MTD is defined based on the rate of DLTs and the MAD is the highest dose administered.

Secondary Objectives	
To select the recommended Phase 2 dose (RP2D) for SL-172154 when administered by intratumoral injection (ITI)	Based on review of all data collected during dose escalation and the pharmacodynamic cohort including safety, tolerability, PK, anti-tumor activity, and pharmacodynamic effects.
To assess preliminary evidence of anti-tumor activity of SL-172154 when administered by ITI	Response per investigator assessment according to Response Evaluation Criteria in Solid Tumors version 1.1 (RECIST v1.1).

	
 ▪ Objective response rate (ORR) (proportion of subjects whose best response is a complete response [CR] or partial response [PR]) ▪ Time to response (TTR): time from the first dose until the first response (CR or PR, whichever is recorded first) that is subsequently confirmed ▪ Duration of response (DOR): time between first response (CR or PR, whichever is recorded first) that is subsequently confirmed and date of disease progression ▪ Change from baseline lesion diameter for injected lesion ▪ Change from baseline lesion diameter for non-injected lesion
To evaluate anti-drug antibodies (ADA) to SL-172154 when administered by ITI during and after treatment.	
 ▪ Number/proportion of subjects with positive ADA titer ▪ ADA duration ▪ Transient vs. persistent ADA

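### SAP 8.1, like protocol 9.2.4, can report an MTD from an escalation that never reached an endpoint, although the SAP was revised because enrollment stopped early

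*SAP*

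**What the plan says.** SAP 8.1: "A MAD will be reported if the DLT rate never reaches" 25% or more; in all other cases an MTD is reported. The estimate is "based on the DLTs observed in the DLT evaluable subjects", by isotonic regression against a 30% target. The worked example is framed for a finished study: "suppose that when the trial is completed, the observed DLT rates" at five dose levels are then listed.

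Protocol 9.2.4: "A MAD will be reported if the observed DLT rate is <25% among all dose levels"; otherwise an MTD. It adds that "the MTD is the dose for which the isotonic estimate of the DLT rate is closest to the target DLT rate of 30" percent.

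SAP section 2 makes identification of the MTD or MAD part of the primary objective and states that "the MAD is the highest dose administered".

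SAP section 1: "As of 24February2022, the study enrollment was prematurely discontinued". It adds that the SAP was updated for this. SAP sections 9 and 10 do make the PK, ADA and biomarker analyses conditional on the assays being run. Section 8.1 contains no comparable condition for an escalation that was cut short.

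**The concern.** An MTD is a claim that the design located a dose with a DLT rate near 30%. A MAD claims only that a given dose was the highest administered. Section 8.1 switches between the two on a single test: whether a dose's DLT rate is at or above 25%. With cohorts of about three, one DLT in a first cohort is 33% and trips the switch, while the decision table says that more subjects are needed at that dose. If enrollment stops there, part of the primary conclusion would state a finding that the design had not made.

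There is a second, smaller issue of wording. The SAP says the rate must never reach 25%, where the protocol speaks of the observed rate at all dose levels. Because DLTs are counted after each cohort, the SAP phrase could be taken to include interim rates. Protocol 16.1 foresees such a path: "If 1/6 subjects with a DLT (no subject with a DLT in cohort #2), then dose escalate to the next higher dose level", that is, 1/3 followed by 1/6.

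**Working it through.** **Inputs.** The 25% cut-off and the fallback come from SAP 8.1 and protocol 9.2.4. The 30% target with nearest-dose selection comes from protocol 9.2.4 and SAP 8.1. The decision table, Beta(1,1) prior, 0.25–0.35 stay interval, cohorts of about 3 and maximum of 12 per dose come from SAP 3.2 and Table 2 (protocol 9.1, Table 5). True DLT rates and stopping points are assumptions; the documents give none.

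**1. The plan's own figures.** For (0/3, 1/3, 0/3, 4/15, 2/4), pooling Levels 2 and 3 gives (1+0)/(3+3) = 16.7%. The estimates are 0, 16.7, 16.7, 26.7 and 50%, at distances of 30, 13.3, 13.3, 3.3 and 20 points from 30%. Level 4 is selected, as the SAP states. Rebuilding the decision table from its stated rules matches 73 of 75 cells. The other two (3/12 and 4/12) compute as stay and are explained by the forced choice at 12 subjects.

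**2. Enrollment stops at 1/3.** Table 2: stay. Reporting rule: 33% ≥ 25%, so an MTD. For (0/3, 1/3) it names Level 2, for (0/3, 0/3, 1/3) Level 3, and for 1/3 at Level 1, Level 1.
- The posterior is Beta(2,3), with P(rate < x) = 1 − (1−x)⁴ − 4x(1−x)³.
- x = 0.25: 1 − 0.316 − 0.422 = 0.262. x = 0.35: 1 − 0.179 − 0.384 = 0.437.
- So 26.2% lies below 25%, 17.5% in 25–35%, and 56.3% above 35%.
- Exact 95% CI for 1/3: 0.8% to 90.6%.

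**3. Enrollment stops at (0/3, 2/3).** Table 2: de-escalate, so the next subjects would go to Level 1. Reporting rule: 67% ≥ 25%, so an MTD. The distances from 30% are 30 points (Level 1) and 36.7 points (Level 2), so Level 1, with no DLTs in three subjects and not re-tested, is named.

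**4. How often, under assumed rates.** Let p be the same true rate at every dose.
- Stop after 3 subjects: P(exactly 1 of 3) = 3p(1−p)². This is 13.5% at p = 5%, 24.3% at 10% and 38.4% at 20%.
- Stop after 6 subjects, p = 10%: 0/3 then at least one DLT of 3 at Level 2 is 0.729 × 0.271 = 0.198; 1/3 then 1/3 at Level 1 (2/6, stay) is 0.243 × 0.243 = 0.059. The total is 25.7%.
- Simulation (10,000 trials per scenario) of an MTD reported with escalation unfinished, for stops after 3, 6 and 9 subjects: 25, 26 and 25% at p = 10%; 13, 14 and 15% at p = 5%; 14, 24 and 41% with true rates rising 5, 10, 20, 30% over the four levels. The simulation treats a de-escalate decision at Level 1 as finished.

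**5. The wording difference.** On final cumulative observed rates, no dose reaching 25% and every dose being below 25% are the same condition, so disagreement is zero. If interim rates counted, a dose going from 1/3 to 1/6 (16.7%), with every other dose below 25%, would give a MAD under the protocol and an MTD under the SAP.
- Stop after 3 subjects: no disagreement, because interim and final are the same.
- Stop after 6 subjects: 1/3 then 0/3 at Level 1 is 0.243 × 0.729 = 17.7% of trials at p = 10%, and 0.135 × 0.857 = 11.6% at p = 5%.
- Escalation run to completion (simulated): an MTD in 71% of trials counting interim rates against 18% on final rates at p = 10%, and 46% against 4% at p = 5%.

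**The case against.** A reader might infer that the SAP replaced the protocol's rule with a different one. The documents do not support that. Both use the 25% cut-off, the same fallback, the DLT evaluable population and isotonic selection at 30%. The natural meaning of the SAP phrase is that no dose level reaches 25%: the sentence before it refers to observed DLTs, the example uses rates at trial completion, and SAP 5.1 handles interim counts separately and cumulates all evaluated subjects at a dose. Nothing in 8.1 directs a search of interim looks. The large completed-trial contrasts in step 5 need both the interim reading and a completed escalation, and this trial's enrollment was cut short. What stands is loose wording.

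The missing completion condition is also not a SAP departure, since protocol 9.2.4 has the same gap. The SAP is nonetheless the place to close it, because it is the document that says it was revised for the early stop.

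It can fairly be said that the harm is limited. SAP 8.1 also requires DLT counts and percentages by dose level, so a 1/3 basis would be visible, and RP2D selection rests on the totality of data. That reduces the consequence but does not make the label correct.

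**Conclusion.** The concern holds in this form: followed literally, SAP 8.1 and protocol 9.2.4 name an MTD whenever any dose stands at or above 25%, whether or not the escalation reached an endpoint. At 1/3 the posterior probability that the dose lies in the design's own 25–35% band is 17.5%. Under an assumed 10% DLT rate at every dose, about a quarter of trials stopped after 3, 6 or 9 subjects would carry an undetermined MTD.

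A reader might also infer that this trial did report a false MTD. That cannot be concluded. The documents give no DLT counts at the stop, and if no dose was at 25% or more the rule yields a MAD. The frequencies in step 4 rest on assumed true rates and stopping points, and on end-of-escalation rules that the documents do not fully define. The 1/3 and (0/3, 2/3) results need none of these assumptions. The wording issue is a clarification, not a conflict.

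**What to change.** Replace the MAD/MTD sentences in SAP 8.1 with:

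> Report a MAD if the final cumulative observed DLT rate is below 25% at every dose level. Report an MTD only if dose escalation reached an endpoint under the Table 2 rules. In every other case, including when enrollment ended while those rules still called for further subjects at the current or a lower dose, report the MTD as not determined, and report the highest dose administered (MAD) with DLT counts and exact 95% CIs by dose level.

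The catch-all also covers 3/12, where the table says escalate but the rate is not below 25%. The SAP should list what counts as an endpoint, including how to label a trial in which Table 2 rejects the lowest dose. It should note the change from protocol 9.2.4, because protocol 9.2 asks for deviations to be documented in the SAP and final report. If the database is already frozen, the same statement belongs in the clinical study report.

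The cost is a few sentences and no new data. The downside is that the trial may have to state that no MTD was determined, even where a dose stopped at stay with a rate near 30%, such as 3/9. The counts and intervals would still show that evidence, and would keep a MAD from being read as a tolerated dose after a result such as 2/3.
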